- f. Neurodevelopmental assessment at 18-24 months corrected age
 - i. Bayley Scales of Infant and Toddler Development III (BSID-III)
 - ii. Modified Checklist for Autism in Toddlers (M-CHAT)
 - iii. Child Behavior Checklist (CBCL)

Individual Infant Timeline:

 2. Study supplement given (within 24 hours of enrollment for total 2 weeks or until enteral intake is at 100 cc/kg/day) 3. Data collection throughout the NICU course (Growth parameters, fluid and nutrition intake and important hospital events), also includes interview with mother to record demographic information and maternal characteristics 4. Blood carnitine panels – drawn at study enrollment and at the end of the intervention (and again if a blood transfusion is administered within this period) 5. Amplitude-integrated EEG readings – within 2-3 of study enrollment and at 28, 32, 36 and 40 weeks' post-menstrual age (dashed lines) 6. Hearing screens – OAE and BAER during the NICU course 7. Brain MRI at 36-40 weeks' GA 8. NNNS at term-equivalent follow-up visit 	1	Study Enrollment (within 72 hours of birth)	Birth	
 24 hours of enrollment for total 2 weeks or until enteral intake is at 100 cc/kg/day) 3. Data collection throughout the NICU course (Growth parameters, fluid and nutrition intake and important hospital events), also includes interview with mother to record demographic information and maternal characteristics 4. Blood carnitine panels – drawn at study enrollment and at the end of the intervention (and again if a blood transfusion is administered within this period) 5. Amplitude-integrated EEG readings – within 2-3 of study enrollment and at 28, 32, 36 and 40 weeks' post-menstrual age (dashed lines) 6. Hearing screens – OAE and BAER during the NICU course 7. Brain MRI at 36-40 weeks' GA 8. NNNS at term-equivalent follow-up visit 				0 hours
 3. Data collection throughout the NICU course (Growth parameters, fluid and nutrition intake and important hospital events), also includes interview with mother to record demographic information and maternal characteristics 4. Blood carnitine panels – drawn at study enrollment and at the end of the intervention (and again if a blood transfusion is administered within this period) 5. Amplitude-integrated EEG readings – within 2-3 of study enrollment and at 28, 32, 36 and 40 weeks' post-menstrual age (dashed lines) 6. Hearing screens – OAE and BAER	2.	24 hours of enrollment for total 2 weeks		72 hours

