We will assess neurodevelopmental outcomes at 18-24 months corrected age using the Bayley Scales of Infant and Toddler Development, Third Edition (BSID-III). The BSID-III is a validated instrument used for assessing the development of Cognitive, Language (Receptive and Expressive), Motor (Fine and Gross), Social-Emotional and Adaptive skills in infants and toddlers. This normative assessment yields scaled scores, composite scores, percentile ranks, and developmental age equivalents, all of which provide important information about a child's level of functioning relative to his or her same-age peers. While Cognitive, Language and Motor skills are assessed through direct interaction with the child, Social-Emotional and Adaptive skills are obtained from parent report. Because the BSID-III is commonly used for identifying children who are in need of early intervention due to developmental delays, this instrument will be sensitive to detecting the types of developmental issues we often see in very young children born preterm. Additionally, at the follow-up visit at 18-24 months corrected age, we will administer two parental questionnaires: the Modified Checklist for Autism in Toddlers (M-CHAT) and the Child Behavior Checklist (CBCL). M-CHAT is a parent-report checklist developed to screen children for early signs of autistic features. The CBCL is a standardized, well-validated parent-report questionnaire developed to assess various maladaptive behavioral and emotional problems in young children.

Record confidentiality: Records relating to the study will be kept in a secure location, to which only study personnel will have access. Records will be kept in a locked file cabinet in the neonatology offices and in a password-protected computer.

Statistical Analyses:

Statistical analysis will be performed with the assistance of a statistician.

Sample size:

We plan to recruit a total of 150 infants for our study over approximately 36months' time. This number is based upon an expected attrition of approximately 50 infants over the course of the study and a desired sample size of 100 infants. The inclusion of 100 infants in our study (50 in each study arm) will allow us to detect a moderate difference in our primary outcomes at a significance level of 0.05 with a power of 0.8. (0.5 SD; α = .05; power = .80).

Primary Outcomes	Mean	Standard Deviation	0.5 x Standard Deviation
Percent weight loss*	10.8%	6.2	3.1
Time to regain	11.3 days	4.3	2.2
birthweight*			

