The effect of L-carnitine supplementation on outcome measures in enrolled infants will be examined for significance by comparing the two groups using unpaired data analysis with the assistance of a statistician. Continuous data (percent weight loss, time to regain birthweight, NNNS score, BSID-III scores) will be compared between the "placebo" and the "carnitine supplemented" groups by unpaired student t-test (a 2 tailed P value <0.05 will be considered to indicate statistical significance) or Wilcoxon's rank sum test for non-parametric parameters. Unmatched nominal data will be compared using Fisher's Exact Test or Chi-square test as required (e.g.: presence or absence of normalization of the carnitine profile; or presence or absence of pathological findings on the discharge MRI). Logistic regression models will be used to adjust for potentially confounding factors including gestational age, birth weight, race, gender, Apgar scores.

Risks and Discomforts:

A brief description of the risks and discomforts associated with this study is included in the protocol consent form and will be discussed in detail with each family at the time of study enrollment.

Carnitine is routinely administered with parenteral nutrition in approximately one-third of the neonatal intensive care units in the United States, although not in the Jack D. Weiler Hospital or Montefiore North Division NICU's. Carnitine is FDA-approved, and there have been no reports of severe toxicity from

overdose. Data available from the adult literature reports side effects of mild gastrointestinal symptoms such as gastritis, vomiting, diarrhea or abdominal cramping; body odor; and seizures, in patients with or without a known seizure disorder. These side effects are dose-dependent and might be avoided by slow consumption of the solution or greater dilution. One investigator reported transient elevation of triglycerides and increased platelet aggregation in uremic patients with severe renal insufficiency who received high doses of carnitine supplementation.⁵²

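### With 50 analysed infants per arm, the plan's two-tailed t-test at 0.05 has power of about 0.70 for a 0.5 SD difference, not the stated 0.80

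*Combined protocol and SAP*

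**What the plan says.** Under Statistical Analyses, Sample size, the plan recruits 150 infants, a number resting on an "expected attrition of approximately 50 infants over the course of the study and a desired sample size of 100 infants". The 100, or "50 in each study arm", is therefore already net of losses. The paragraph states that this number "will allow us to detect a moderate difference in our primary outcomes at a significance level of 0.05 with a power of 0.8", and gives the parameters as "0.5 SD; α = .05; power = .80". Sidedness is not mentioned. The table that follows lists each primary outcome with its SD and a column headed "0.5 x Standard Deviation": 3.1 for percent weight loss (SD 6.2), 2.2 days for time to regain birthweight (SD 4.3), and half-SD values for 13 NNNS scales.

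The Outcome Measures section compares percent weight loss, time to regain birthweight and NNNS scores between arms by unpaired t-test, where "a 2 tailed P value <0.05 will be considered to indicate statistical significance". The Wilcoxon rank sum test is the alternative for non-parametric data.

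The Timeline of Assessments ends with "Neurodevelopmental assessment at 18-24 months corrected age", so attrition over the whole study covers a much longer period than the primary outcomes, the last of which is the NNNS at 40 weeks postmenstrual age.

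**The concern.** The power statement and the analysis section describe the same outcomes and the same nominal 0.05 level, but the stated power does not belong to the stated test. An effect of 0.5 SD with 50 per arm is a standard configuration, and a two-sided 0.05 test there falls well short of 0.80.

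This paragraph is the trial's only justification of its size. If the figure is wrong, a null result will be read as though a half-SD difference had been sought with an 80% chance of finding it, when the chance was nearer 70%. The half-SD column also becomes a list of differences that the trial cannot detect with the power claimed.

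**Working it through.** **Inputs.** From Sample size: n = 50 per arm after attrition, equal allocation, d = 0.5 (difference divided by SD), alpha 0.05, stated power 0.80. From Outcome Measures: unpaired t-test, two-tailed. From the table: SD 6.2 for percent weight loss and 4.3 days for time to regain birthweight.

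**Step 1: power at 50 per arm.** The noncentrality parameter is d × √(n/2) = 0.5 × √25 = 2.5, with 2n − 2 = 98 degrees of freedom.

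| Test | Normal approximation | Noncentral t |
|---|---|---|
| Two-sided 0.05 | Φ(2.5 − 1.960) = 0.705 | 0.697 |
| One-sided 0.05 | Φ(2.5 − 1.645) = 0.804 | 0.799 |
| Two-sided 0.10 | not needed | 0.799 |

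A simulation of 200,000 trials of the two-sided 0.05 test also gives 0.697. The plan's 0.80 is reproduced only by the second or third row, and the plan specifies neither. A sidedness slip is the likely origin, but that is an inference, since the documents do not show the calculation.

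**Step 2: number needed for 0.80, two-sided 0.05.** The normal formula gives n = 2 × (1.960 + 0.842)² / 0.5² = 62.8, so 63 per arm. The t-test calculation gives 63.77, so 64 per arm (power 0.8015) and 128 in total.

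**Step 3: difference detectable with power 0.80 at 50 per arm.** Solving the noncentral t gives d = 0.566.
- Percent weight loss: 0.566 × 6.2 = 3.5 percentage points (table: 3.1).
- Time to regain birthweight: 0.566 × 4.3 = 2.4 days (table: 2.2).

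**Step 4: how power varies with the number analysed.** For 0.5 SD, two-sided 0.05:

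| Analysed per arm | Power |
|---|---|
| 50 | 0.697 |
| 55 | 0.738 |
| 60 | 0.775 |
| 64 | 0.801 |
| 75 (no loss) | 0.860 |

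**Step 5: loss that can be tolerated.** 150 − 128 = 22 infants, or 22/150 = 14.7%. The plan expects about 50/150 = 33.3% lost over the whole study.

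**Step 6: do other readings rescue 0.80 at 50 per arm?**
- *Rounded table values.* Taking 2.2/4.3 = 0.512 SD gives 0.717. The NNNS Handling row, 0.14/0.27 = 0.519 SD, gives 0.728. Only Stress Abstinence passes 0.80 (0.844), because half of 0.05 is shown as 0.03, which makes it 0.6 SD.
- *Wilcoxon test.* Under normality, with an assumed relative efficiency of 0.955, power is about 0.68.
- *Covariate adjustment.* Reaching 0.80 would need covariates explaining 1 − (0.5/0.566)² = about 22% of outcome variance. The Sample size paragraph assumes no adjustment, and the named test for these outcomes is unadjusted.

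All these figures are for one comparison at an unadjusted 0.05.

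**The case against.** The best defence has three parts.

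**Sidedness.** The Sample size paragraph is silent on it, and the Hypothesis section is directional. Read as one-sided at 0.05, the paragraph's arithmetic is right (0.799). That locates the error but does not remove it: the Outcome Measures section fixes two tails for the same outcomes, and no one-sided test appears anywhere. Read one way the two sections conflict; read the other way the number is wrong.

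**More than 100 infants may be analysed.** All three primary outcomes are complete by about 40 weeks postmenstrual age, while the expected loss of 50 runs to 18-24 months. With 64 or more per arm, power is at least 0.80. This point stands as a limit on the practical effect, most clearly for the early growth outcomes. But the plan gives no attrition by time point, the mortality it reports for the youngest infants occurs early enough to matter, and its claim is made at 50 per arm, where it is wrong whatever retention turns out to be.

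**Stratified randomization.** Strata are defined by gestational age and SGA status, and balancing prognostic strata raises the power of even an unadjusted t-test when the true effect is this large. In a simulation assuming perfect balance, and strata explaining 10% to 50% of the variance (an assumed range), power at 50 per arm is 0.71 to 0.76. So 0.70 is approximate and may be slightly low, but 0.80 is still not reached.

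A further caution concerns wording. Under Randomization, one infant of each multiple-birth set is chosen for the analysis, so an infant may have complete data and not be analysed. Any condition on numbers should therefore be written in terms of infants analysed.

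**Conclusion.** The stated power is wrong for the test that the plan specifies. At 50 analysed per arm, power for 0.5 SD is about 0.70, ten points below the 0.80 claimed, and the risk of missing such a difference is about 30% rather than 20%. Power 0.80 requires 64 analysed per arm, or a true difference of about 0.57 SD. The gap is too large to come from rounding or from the choice between normal and t formulas.

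The result assumes equal arms, approximately normal outcomes with the tabulated SDs, an unadjusted two-sided t-test, and no multiplicity adjustment across the primary outcomes. An outcome for which at least 128 infants are analysed would have the 0.80, but the plan neither states that condition nor shows that it will be met. As the only justification of sample size, the figure must be corrected.

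**What to change.** State the sidedness in the Sample size paragraph and replace the power claim with wording such as:

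> With 50 analysed infants per arm and a two-sided alpha of 0.05, unadjusted and per comparison, power is about 0.70 for a difference of 0.5 SD. Power of 0.80 corresponds to about 0.57 SD (about 3.5 percentage points of weight loss and 2.4 days to regain birthweight). An outcome has power 0.80 for 0.5 SD only if about 128 of the 150 recruited infants are analysed for it.

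The table's half-SD column should no longer be presented as the difference detectable with power 0.80 at 50 per arm.

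The cost is a text edit and a less favourable headline figure. It needs no extra infants and no change to the analysis. If the sponsor prefers to keep 0.80 at 0.5 SD with the same one-third loss, recruitment would have to rise to 128 / (2/3) = 192. That is a choice, and the correction does not depend on it.

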We hypothesize that preterm infants supplemented with early physiologic doses of L-carnitine while on parenteral nutrition will have improved short-term growth parameters and significantly higher neurobehavioral scores when compared with control infants.

Primary Aims:

To determine whether carnitine supplementation is associated with:

- 1. Decreased percent weight loss within the first two weeks of life and decreased length of time to regain birthweight.
- 2. Improved performance on the NICU Network Neurobehavioral Scale (NNNS) at 40 weeks postmenstrual age (+/- 2 weeks).

Secondary Aims:

To determine whether carnitine supplementation is associated with:

- 1. Increased rate of growth of head circumference within the first month of life and increased food efficiency (weight gain/calorie intake) during the supplementation period.
- 2. Normalization of the serum carnitine profile at two weeks of life, compared with infants born at a post-menstrual age 2 weeks later.
- 3. Enhanced brain maturation as measured by amplitude-integrated EEG (aEEG) measurements obtained during the hospital course
- 4. Fewer abnormal findings, better brain growth, white matter development and brain metabolism on brain magnetic resonance imaging (MRI) at 36-40 weeks' corrected age (prior to hospital discharge)

Because of the potential for systemic effects of L-carnitine supplementation, we will also monitor those variables which showed significant difference in our prior study: rates of proven infection, hearing screen failure and PDA ligation.

Primary Outcomes:

- 1. Length of time to regain birthweight,
- 2. Percent weight loss in the first two weeks of life,
- 3. Neurodevelopmental scores on the NICU Network Neurobehavioral Scale (NNNS) at 40 weeks post-menstrual age (+/- 2 weeks)

Methods/Design:

This is a prospective, randomized controlled clinical trial involving infants with gestational age (GA) <32 wks who are born at either the Jack D. Weiler Hospital or the Wakefield Division of Montefiore and admitted to theirNeonatal Intensive Care Unit. Informed consent will be obtained from the parents of eligible patients as early as possible within 72 hours of birth. Infants whose parents have signed an informed consent form will be randomized to receive either carnitine supplementation (50 µmol/kg/day) versus placebo within 72-96 hours of birth.

Inclusion criteria:

- Infants born <32weeks' gestation
- Exclusion criteria:
 - Presence of

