NNNS Scores**			
Habituation	7.91	1.14	0.57
Attention	5.30	1.04	0.52
Arousal	4.16	0.81	0.41
Regulation	5.00	0.82	0.41
Handling	0.27	0.27	0.14
Quality of Movement	3.81	0.78	0.39
Excitability	4.23	2.10	1.05
Lethargy	6.32	3.24	1.62
Nonoptimal Reflexes	4.32	1.73	0.87
Asymmetry	1.93	1.33	0.67
Hypertonicity	0.07	0.26	0.13
Hypotonicity	0.55	0.76	0.38
Stress Abstinence	0.15	0.05	0.03

Power Calculation:

*Data available from Jack D. Weiler NICU retrospective analysis (2010)

**Tronick, E. Z., K. Olson, et al. (2004). "Normative neurobehavioral performance of healthy infants on the Neonatal Intensive Care Unit Network Neurobehavioral Scale." Pediatrics 113(3 Pt 2): 676-678.

Baseline Comparability:

Distribution of all variables will be examined for normality. Mean (continuous variables), or median (ordinal data and not normally distributed data) will be used as measures of central tendency. Range, percentiles, variance and standard deviation will be used as measures of dispersion. Standard error of the mean and 95% confidence intervals will be calculated to estimate the true populations mean for the placebo and the carnitine supplemented group. Frequency distribution will be presented as grouped, as well as relative frequency. Bivariate distributions will be presented using contingency tables. Descriptive statistics of infant's characteristics at baseline will be compared between carnitine supplemented and placebo group using t-tests for continuous variables (birthweight, age at enrollment) and chi-square test for categorical variables (race, sex, prenatal care, multiple gestation, type of delivery).

Outcome Measures:

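### The 0.80 power claim is not available for an improvement in Hypertonicity: on the tabulated values the half-SD target (0.13) exceeds the mean (0.07)

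*Combined protocol and SAP*

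**What the plan says.** The Primary Outcomes list names "Neurodevelopmental scores on the NICU Network Neurobehavioral Scale (NNNS) at 40 weeks post-menstrual age (+/- 2 weeks" without singling out a scale, and the second primary aim is better performance on that instrument.

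The Sample size section says: "The inclusion of 100 infants in our study (50 in each study arm) will allow us to detect a moderate difference in our primary outcomes". The effect size and error rates follow in brackets as "0.5 SD; α = .05; power = .80". Recruitment of 150 rests on an "expected attrition of approximately 50 infants over the course of the study and a desired sample size of 100 infants".

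The table that follows has a column for primary outcomes and lists 13 NNNS scales, each with a mean, an SD and half the SD. The row for "Hypertonicity" reads "Hypertonicity 0.07 0.26 0.13". The footnote attributes the NNNS figures to published norms for healthy infants. No row is exempted from the power statement.

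The Outcome Measures section assigns NNNS scores to the "unpaired student t-test (a 2 tailed P value <0.05 will be considered to indicate statistical significance", with Wilcoxon's rank sum test as the alternative. Fisher's exact test and the chi-square test are reserved for nominal data.

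**The concern.** For Hypertonicity the difference to be detected is larger than the mean from which it would be subtracted. Taken as an improvement, the direction of the primary aim, it would put the carnitine mean below zero. The mean and SD also look like those of a score that is nearly always 0, for which a half-SD argument is a poor guide.

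The sentence "will allow us to detect a moderate difference in our primary outcomes at a significance level of 0.05 with a power of 0.8" covers this scale as it covers the rest. A reader of the final report could then take a null result on Hypertonicity as coming from a test with 0.80 power, when on the planning figures the trial would more likely than not miss even complete elimination of hypertonicity.

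**Working it through.** **Inputs.** Mean 0.07, SD 0.26, half-SD 0.13 (power table); 50 per arm, α = 0.05, power 0.80, effect 0.5 SD (Sample size); two-tailed t-test or Wilcoxon (Outcome Measures).

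**The plan's own figure.** Normal approximation: power = Φ(d / √(2/n) − z), where d is the difference in SDs. With d = 0.5 and n = 50, d / √(2/50) = 0.5 / 0.2 = 2.5.
- Two-sided: Φ(2.5 − 1.960) = 0.705 (noncentral t: 0.697).
- One-sided: Φ(2.5 − 1.645) = 0.804 (noncentral t: 0.799).

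The stated 0.80 reproduces only with a one-sided test, whereas the analysis is two-tailed. That is a separate and broader matter affecting every outcome. It means that 0.80 is already a generous benchmark here.

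**Is the target attainable?**
- Half-SD: 0.5 × 0.26 = 0.13, which is 0.13 / 0.07 = 1.86 times the mean.
- Implied carnitine mean: 0.07 − 0.13 = −0.06.
- Largest possible reduction with a floor of 0: 0.07, or 0.07 / 0.26 = 0.27 SD.
- Rounding does not help: the mean is at most 0.075 and half the SD at least 0.5 × 0.255 = 0.1275.
- Hypertonicity is the only one of the 13 NNNS rows in which half the SD exceeds the mean. The next closest is Hypotonicity, at 0.38 / 0.55 = 0.69.

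**Power if carnitine removed all hypertonicity (50 per arm, two-sided 0.05).**

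1. *t-test approximation, SD 0.26 in both arms.* 0.2692 / 0.2 = 1.346; Φ(1.346 − 1.960) = 0.27 (noncentral t: 0.27). Over the rounding limits of the mean and SD the range is 0.23 to 0.31. Reaching 0.80 for this reduction would need 2 × (1.960 + 0.842)² / 0.2692² = 217 per arm.

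2. *Score treated as 0/1.* A 0/1 variable with 7% positive has SD √(0.07 × 0.93) = 0.255, close to the tabulated 0.26. Let control events X follow Bin(50, 0.07) and set every carnitine infant to 0. The tests then differ in how many control events they need:

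| Test | Largest X not significant | Smallest X significant | Power |
|---|---|---|---|
| t-test | 3 (p = 0.080) | 4 (p = 0.042) | P(X ≥ 4) = 0.47 |
| Wilcoxon | 3 (p = 0.080) | 4 (p = 0.042) | P(X ≥ 4) = 0.47 |
| Fisher's exact | 5 (p = 0.056) | 6 (p = 0.027) | P(X ≥ 6) = 0.135 |

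The 0.27 and 0.47 differ because the first keeps an SD of 0.26 in the carnitine arm, while an all-zero arm has SD 0. All three figures are well below 0.80.

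**The case against.** Four points can be made for the plan.

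*The floor and direction are not in the documents.* Correct. Nothing states the range of the Hypertonicity score or which end is favourable. The name of the scale and the match between 0.26 and 0.255 make a mostly-zero score with low values favourable the natural reading, but it remains an assumption.

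*The mean of 0.07 is not stated to be the placebo mean.* Also correct. It is a healthy-infant norm, and the trial enrols infants born before 32 weeks, whose mean may be higher. With SD held at 0.26, a reduction of 0.13 becomes possible once the control mean reaches 0.13. For a 0/1 score, where the SD moves with the mean, it needs p ≥ 0.5 × √(p(1 − p)), which solves to p ≥ 0.20. A reader might therefore infer too much by calling the target impossible outright. But the plan offers no preterm value, so this argues for replacing or qualifying the row rather than leaving it as it is.

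*The test is two-tailed and the text speaks of a difference.* A worsening from 0.07 to 0.20 can occur. The point therefore concerns improvement only, which is what the primary aim seeks.

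*It is one scale among many.* True. The sample size is set generically at 0.5 SD, and nothing in this row drives it.

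A reader might also take the Fisher figure of 0.135 as the size of the problem. The documents do not support that: NNNS scores are assigned to the t-test or Wilcoxon, for which the same scenario gives 0.47.

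**Conclusion.** The power statement does not hold for an improvement in Hypertonicity on the plan's tabulated values. At the largest improvement available, power is about 0.27 to 0.47 with the tests the plan assigns, and 0.135 with Fisher's exact test, against a stated 0.80.

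This rests on three assumptions: a floor of 0, lower scores being better, and 0.07 as the placebo mean. The 0.47 and 0.135 also treat the score as 0/1. The arithmetic is secure; the assumptions are plausible but not documented.

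A reader might infer that the whole sample size fails, or that no effect on this scale could ever be detected. Neither follows: the defect lies in one of 13 NNNS rows, a worsening remains possible, and a higher control mean could bring the target within reach.

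**What to change.** - In the Sample size section, exclude Hypertonicity from the outcomes for which 0.80 power to detect a half-SD improvement is claimed.
- Add to the table note that a half-SD target does not apply to a scale at its floor, and that the NNNS planning values are healthy-infant norms rather than expected values for very preterm controls.
- Label Hypertonicity as descriptive. Keep the t-test or Wilcoxon comparison already planned, and add the proportion of infants with any hypertonicity in each arm as a summary. Do not replace the comparison with Fisher's exact test: in the scenario above that would lower power from 0.47 to 0.135.

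The cost is a table edit, a sentence or two of text, and a less favourable power statement for one of the 13 NNNS scales. The sample size and the other analyses do not change.
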